3.4. Timing of analyses

All analyses will be done after database lock. No interim analyses are planned. Database lock is planned in the third quarter of 2019 and analyses are planned subsequently.

| Outcome | Origin of data | Timing of data collection |
|--|--|---------------------------|
| Primary outcome (appropriateness) | Laboratory Information System (LIS) | 05-12/2018 |
| Secondary outcome (diagnostic error) | Primary care electronic health record (EHR) and telephone interviews | 07/2018-06/2019 |
| Secondary outcome (volume) | LIS | 06/2019 |
| Exploratory outcome (cascade activities) | Primary care EHR and LIS | 07/2018-06/2019 |

Table 1: Timing of outcome assessments

4. Data capture system

The data collection tool used in this trial was designed by Healthdata, a division of Sciensano (formerly known as the Scientific Institute for Public Health). The data capture system includes the following:

- Data collection form (HD form)
- Data collection tool (HD4DP)
- Data pseudonymization
- Data encryption
- Data validation tool (HD4RES)
- Datawarehouse

Figure 2 provides a schematic overview of the data capture system and its specific stages.

[figure not shown]

Figure 2: Overview of data capture system. From <http://www.Healthdata.be>.

The full description of the data capture system has been described in an earlier document[4] and have been reviewed and authorized by the Sector Committee for Social Security and Health of the Privacy Commission on May 16, 2017. In short, the investigators collect study data directly in their primary source. From this primary source a semiautomated export is programmed into the data collection form. For all investigators, the layout of this data collection form is similar. After a first automated data export, specific data elements can be completed manually directly in the data collection form. The form contains optional and mandatory fields and can only be completed when all mandatory fields have been completed. Once completed and validated by the investigator, the form is encrypted and sent to a trusted third party (TTP). For this trial, the eHealth Codage service acts as TTP. The TTP uses a hashing algorithm to pseudonymize the unique identifier of the patient. After this hashing, the data is again encrypted and sent to the Healthdata platform. The data is first received in a validation environment, where it can be viewed, queried and validated. When validated, it can consequently be imported into the data warehouse.

4.1. Data security

Study investigators have access only to the HD4DP tool. This tool is implemented within the EHR or LIS. Access to the tool is granted after the investigator has opened his EHR or has accessed the LIS. No additional authorization is required to access HD4DP. The data collection form is made accessible from within this tool by Healthdata after validation by the research team project manager. At this time, investigators can start collecting data from the primary source and submitting it to Healthdata. Data submitted to Healthdata through HD4DP is encrypted using eHealth encryption tools and can only be decrypted by the eHealth Codage service and Healthdata.

The eHealth Codage service pseudonymizes the patient identifier (social security number) using a hashing algorithm. To prevent security breaches, all patient sensitive data except for the unique identifier

are coded at the primary source. Moreover, except for process logs, no sensitive data is stored at the TTP. After coding of the patient unique identifier, the data is again encrypted using eHealth encryption tools and transferred to Healthdata.

After decryption, the data is stored in the validation environment of Healthdata. Access to the data is managed by Sciensano. The study administrator at Sciensano is responsible for authorization of access after validation by the chief investigator. Access to the data is organized through a two-factor identification including a personal password and an SMS code. Users have differentiated access according to their access/read/write rights depending on their role in the research team.

4.2. Server security

All data are stored on the servers of Healthdata. The servers are hosted at the Arxus Nv datacentre and have been tested and audited by independent engineers. Internal safety measures are under the responsibility of the Healthdata data protection officer. Detailed information on the privacy and safety measures of the Healthdata servers can be found on <https://healthdata.sciensano.be/en/information-security-privacy>.

4.3. Queries

The data collection form is programmed to allow only structured data and queries are in fact automated on the level of the data collection form. When critical fields are missing or values exceed certain limits, the data collection form will flag data elements and submitting the form will not be possible. At the top of the data collection form for an individual patient, an overview of open comments is visible in a colored line. When all the red fields in the colored line have disappeared, there are no more open comments for the patient, and the form can be submitted.

Once the data for an individual patient is submitted, manual queries can be run in the database to verify data completeness or veracity of the data. A manual query will be programmed to monitor the data collection per physician. Each time the query is run, the results will be documented in a spreadsheet specifically designed to monitor the data collection progression.

5. Data monitoring and review

As specified in the protocol, due to the nature of the collected data (pseudonymised data from data providers), no data monitoring of source documents is possible.

Data collected from the laboratory information systems will be reviewed based on the number of collected informed consent forms. Due to the pseudonymisation of the data in the data collection form, it is not possible to review whether laboratory data for each included patient is collected. We do know how many patients are included per participating physician. This denominator will be used to review the data collection. If for a given physician less data collection forms are collected than the number of informed consent forms in the master file, a notice will be sent to the data provider (laboratory) to review the status of the data collection.

Data collected from the investigators is semi-automatically integrated in the data collection form directly from within the EHR without manual input from the investigator. The protocol specifies that no data monitoring is feasible for this data collection due to the pseudonymized nature of the data. To assist investigators in the use of the data collection form, clinical research assistants (CRAs) are trained in its use in the various EHR systems available in primary care. Differences in database architecture and issues of semantic inoperability across EHR systems could cause the data collection form to misinterpret some of the data entered in the primary source. To avoid this, the CRA's assisted the investigators in the data collection in order to ensure data uniformity and quality. These CRA's have no access to the data within the data warehouse. Again, the denominator of total number in informed consent forms per physician will be used to review the status of the data collection.

For the data collected directly from patients, a CRA is trained to perform structured interviews based on the data elements defined for this data collection. From these structured interviews the data elements will be recorded directly in the data collection form and validated by the CRA. This CRA has no access to the data in the data warehouse.

[figure not shown]
6. Data management

6.1. Database structure

The database for the ELMO study is maintained by Sciensano (Brussels, Belgium), formerly the Institute of Public Health (ISP-WIV) and structured to be accessible with SAS Enterprise Guide software (Copyright © 2019 SAS Institute Inc.). SAS and all other SAS Institute Inc. product or service names are registered trademarks or trademarks of SAS Institute Inc., Cary, NC, USA.

The database consists of 4 parts:

1. KCELABGP_LAB (data provided by clinical laboratories)
2. KCELABGP_GP (data provided by general practitioners)
3. KCELABGP_PAT (data provided by telephone patient interviews)
4. KCELABGP_COM

6.1.1.KCELABGP_LAB

The KCELABGP_LAB database contains the data collected through the ambulatory laboratories. This database contains several tables, each containing data from the same data collections. The tables included in the KCELABGP_LAB database are TU_KCELABGP_LAB, TU_KCELABGP_LAB_INDICATN, TU_KCELABGP_LAB_TST, TU_KCELABGP_LAB_ORD_SETS, TU_KCELABGP_LAB2 and TU_KCELABGP_LAB2_LAB_TST.

TU_KCELABGP_LAB

This table contains data on each individual laboratory panel linked to an individual patient. The table includes information on date of birth, sex, reimbursement codes, physician, date of the laboratory test

panel, date of death (if applicable) and total cost of the laboratory test panel. Each row in this table represents a unique laboratory test panel and a single patient may be represented more than once.

TU_KCELABGP_LAB_INDICATN

This table contains data on the indications for each laboratory test panel. It includes data on the selected indications and the additional information provided by the physician when code 99 was used. Code 99 implied that the physicians reported that an indication was applicable outside of the 17 study indications. The exact nature of this indication was included in a free text field of the CPOE. Each row represents a unique indication. Since many laboratory test panels had more than one indication, most panels are represented multiple times.

TU_KCELABGP_LAB_LAB_TST

This table contains data on all ordered laboratory tests. Data on the laboratory test (either a Logical Observation Identifiers Name and Codes (LOINC) code or a Medidoc code), result of the test, upper limit, lower limit are included. Data on whether the result represents a normal or abnormal value is also included. The laboratory test results can be numeric or alphanumeric so that a wide variety of results are possible. Each row in the table represents a unique test. Each panel is represented multiple times as is each patient.

TU_KCELABGP_LAB_ORD_SETS

This table contains data on the selected order sets. For each possible indication, multiple order sets were developed. For instance, for the indication 'hypertension' an order set was developed for the diagnosis of hypertension, for the follow-up of hypertension and so on. This table includes more detailed information on the exact order set that was selected with respect to the indication.

TU_KCELABGP_LAB2 and TU_KCELABGP_LAB2_LAB_TST

This table has an identical structure to the TU_KCELABGP_LAB and TU_KCELABGP_LAB_LAB_TST tables, but contains data on the patients for which cascade tests were ordered.

6.1.2.KCELABGP_GP

The KCELABGP_GP database contains information collected from the electronic health records (EHR) of the physicians on the patients included in the study. This data was collected directly from within the EHR through an electronic clinical report form (eCRF), called an eForm. Each row coincides with an item on this eForm.

TU_KCELABGP_GP

This table contains data on each eForm. Each row corresponds to an individual eForm and contains information on the patient such as sex, date of birth, date of death (if applicable), number of new diagnoses recorded through the eForm, date of the laboratory test panel, information on why the test was ordered and information on any cascade activities.

Each row in this table represents a unique eForm, so for a single patient there may be multiple rows, as for each included laboratory panel a corresponding eForm was collected. Each row has a unique identification key, named 'TXT_WRKFLOW_IDN', through which all data in this database can be linked to an individual eForm.

TU_KCELABGP_GP_DIAG

This table contains data on the new diagnoses recorded through the eForm. Each row represents a unique diagnosis and includes information on the date of the new diagnosis, information on whether the physician considered the diagnosis as related to the laboratory test (either to the indication of the laboratory test order or to the result of one of the laboratory tests in the panel), whether the new diagnosis was diagnosed timely, the name of the new diagnosis and International Classification of Primary Care (ICPC-2) or International Classification of Diseases (ICD-10) codes.

TU_KCELABGP_GP_DWNSTRM_INV

This table contains data on all the downstream investigations recorded through the eForms. Each row represents a unique downstream investigation and includes information on the patient, the type of investigation and free text additions registered by the physician.

TU_KCELABGP_GP_DOWNSTRM_REF

This table contains information on the downstream referrals recorded in the eForm. Each row represents a unique downstream referral and includes information on the patient and on the specialty of the specialist or other healthcare professional to whom was referred.

6.1.3.KCELABGP_PAT

TU_KCELABGP_PAT

This table is identical in structure to that in the KCELABGP_GP database.

TU_KCELABGP_PAT_DIAG

This table is identical in structure to that in the KCELABGP_GP database.

TU_KCELABGP_PAT_DWNSTRM_INV

This table is identical in structure to that in the KCELABGP_GP database.

TU_KCELABGP_DWNSTRM_REF

This table is identical in structure to that in the KCELABGP_GP database.

TU_KCELABGP_PAT_LAB_TST_ORD

This table is identical in structure to that in the KCELABGP_GP database.

6.1.4.KCELABGP_COM

This database contains tables that are required to be able to map or merge data from the KCELABGP_LAB databases with the KCELABGP_GP databases. The identification key for a patient in the KCELABGP_LAB database is not identical to that in the KCELABGP_GP database (for the same patient). KCELABGP_COM contains the mapping table to link the identification numbers for a single patient across the databases.

6.2. Matching of data across different databases

The data from three different providers and databases are linked through a patient identification key. This allows us to identify the same patient across databases. However, for some patients, multiple laboratory panels are included in the KCELAB_LAB database. Besides the patient identification key, we will also use 'date of laboratory test', a data element present in all three datasets, to link an eForm to its corresponding laboratory panel.

The majority of eForms can be linked automatically based on corresponding patient identifiers and 'date of laboratory test'. However, a substantial number of eForms cannot be linked this way, partly because in the eForms the laboratory date had to be entered manually and was therefore susceptible to typing errors.

We will apply the rules below to be able to manually link the eForms to the corresponding laboratory panels:

- a) If the patient identification key and laboratory test date are identical in the laboratory panel (row in KCELAB_LAB database) and the eForm (row in KCELAB_GP database), then the rows will be matched.
- b) If the patient identification key between the databases are identical and the laboratory panel date in the eForm falls within a period of 14 days before and up to 14 days of the laboratory panel date in the KCELAB_LAB database, then the rows will be matched.
- c) If the patient identification key between the databases are identical and the eForm laboratory date differs exactly 1 year with the laboratory panel date, then the rows will be matched.
- d) If the patient identification key between the databases are identical, but the eForm laboratory date has a reverse day and month notification (DDMM) compared to a non-linked laboratory panel date, then the rows will be linked.

We applied the same procedure to link the patient interviews to the corresponding laboratory panels.

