These levels are important because we will analyse at the level of the patient or the test (depending on the outcome), but we will recruit physicians and allocate primary care practices. We have calculated our sample size and translated this to the amount of physicians to be recruited and the duration of the study. For these calculations we have made several assumptions based on data from various sources ([De Sutter 2007](#), [Janssens 2014](#)). First, we assume that the average test panel will include 5 study tests. Second, we assume that during the study period each test panel will correspond to one patient (that there will be no multiple test panels per patient). Third, we assume that each physician orders blood tests for 15 patients per week. Fourth, we assume that physicians will use the intervention in 70% of the situations (implying a 30% usage of paper-based orders) based on figures by van Wijk et al ([van Wijk 2001](#)). Fifth, we assume that a primary care practice includes 2.35 physicians, based on the recruitment data from an ongoing cluster randomized trial in primary care ([Heselmans 2013](#)).

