Alongside the 17 indications included in the study, physicians had the possibility to add other indications. These indications are included in the database as "99" and a free text field allowed physicians to specify the nature of these indications. In some situations, the free text clearly shows that one or more of the additional indications is in fact one of the study indications. Hence, all references to one or more of the study indications will be recoded from "99" to one of the study indications. Where necessary, a second assessment of the indication will be sought, and if there is any doubt about the indication, it will not be recoded.

6.3.3.KCELABGP_GP

This database contains records that were valid in the past, as well as currently valid records that replace earlier records. Only the currently valid records will be included for further analysis. Furthermore, we will only analyze the data that comes from eForms that can be linked to a corresponding lab panel (see 46.2).

The protocol of this trial states that all new diagnoses made within a period of six months after the laboratory date will be analyzed. Therefore, all diagnoses with a start date before or 6 months after the laboratory date will be excluded. Also diagnoses with unclear labels or where the description clearly indicates that they are not diagnoses but rather treatments or examination will be excluded.

The content of the diagnoses in this table is represented by an ICPC-2 code[8], an ICD-10 code, a free text label or a combination of these three. Since ICPC-2 is the most widely used international classification for systematically recording and analyzing primary care information¹, we will use these codes for further analysis. Therefore, we will complete missing ICPC-2 codes by converting ICD-10 codes or free text labels to their corresponding ICPC-2 code, using the Dutch ICPC-2 and ICPC-ICD10-tables, as well as the Belgian Bilingual Biclassified Thesaurus (3BT), provided by eHealth for all Belgian EHR developers, as conversion tables. All remaining free text labels will be manually recoded to an ICPC-2 code. This will result in an additional tailor-made conversion table named 'DIAG_FREETXT'.

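### SAP 6.2 has no key-only link for a patient with one panel and one eForm, so a received form whose date error fits no rescue rule is dropped

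*SAP*

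**What the plan says.** SAP 6.2 uses a patient key to recognise the same person across the laboratory, physician and interview data. It adds the laboratory date because "for some patients, multiple laboratory panels are included in the KCELAB_LAB database". Most eForms link on key plus identical date. "However, a substantial number of eForms cannot be linked this way". The SAP puts this down in part to mistakes made when physicians typed the date by hand. The rules, all requiring the same key, are:

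- (a) the dates are identical;
- (b) the typed date "falls within a period of 14 days before and up to 14 days of the laboratory panel date";
- (c) "the eForm laboratory date differs exactly 1 year with the laboratory panel date";
- (d) the typed date "has a reverse day and month notification (DDMM) compared to a non-linked laboratory panel date".

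The patient interviews are linked by the same procedure.

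Other sections fix what follows from a failed link:

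- SAP 6.3.3: "we will only analyze the data that comes from eForms that can be linked to a corresponding lab panel". It also removes diagnoses dated before the laboratory date or more than six months after it.
- SAP 10.3: about 15% of patients have no eForm (a preliminary figure), nothing is imputed, and patients without data are excluded.
- SAP 6.1.2: one eForm was collected for each included panel. Protocol 9.1 planned on the basis that "during the study period each test panel will correspond to one patient".
- SAP 7.1: the pre-analysis report lists missing forms by physician, laboratory and EHR system. It asks for no count of forms received but not linked.

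**The concern.** The stated reason for using the date is to tell apart several panels of one patient. Where a patient has one panel and one eForm, there is nothing to tell apart, yet the date condition still applies. A mistyped date outside rules (b) to (d) then removes a completed outcome form, and with it the patient, from the diagnostic-error analysis. That analysis is a non-inferiority comparison already below the size the SAP says it needs. As the SAP stands, the loss would also go unreported. The primary outcome is unaffected, because it comes from the laboratory system (SAP 3.4, Table 1).

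A second gap lies in the order of matching. Only rule (d) is limited to panels not yet linked. Nothing makes rules (a) to (c) one-to-one or sets a tie-break.

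**Working it through.** **1. Which errors fall through, for a single-panel patient.**

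- Month wrong, day and year right: the dates are at least 28 days apart, so (b) fails. The year is the same, so (c) fails. Rule (d) would need the typed day to equal the panel's month and the typed month to equal the panel's day. Since the typed day is the panel's day, the panel's day and month would be equal, and the typed month would then be correct. So (d) fails too, and this error is never rescued.
- Day 02 typed for 20: 18 days apart, so (b) fails, and (c) does not apply. Rule (d) does not apply unless the panel fell in February, and even then it needs the typed month to be 20, which is impossible.
- Year wrong by one and day also wrong by one: not exactly one year, so (c) fails.

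**2. One-to-one matching.** Under (b), an eForm dated midway between two panels of the same patient up to 14 + 14 = 28 days apart satisfies the rule for both.

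**3. The plan's own size.** Inputs from Protocol 9.1.2: error rate 2.5% in both arms, margin 1%, 80% power, physician-level ICC 0.025.

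- Per arm: (1.645 + 0.842)² × 2 × 0.025 × 0.975 / 0.01² ≈ 3,014, so 6,028 in total against 6,032 stated. This reproduces at one-sided 5%. One-sided 2.5% gives 7,654.
- With 280 physicians (SAP 3.3): 280m = 6,032 × [1 + 0.025(m − 1)]. Hence m = 6,032 × 0.975 / (280 − 150.8) = 45.52 and N = 12,746, against 12,740 stated. This reproduces.
- Shortfall at the SAP's check: 12,740 − 11,200 = 1,540.

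**4. Size of the loss.** The share unlinked after (a) to (d) is not in the documents, so a range is assumed.

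- Patients with an eForm: 11,200 × 0.85 = 9,520.
- Lost if 2 / 5 / 10% of these stay unlinked: about 190 / 476 / 952.

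For power, take slightly larger losses, 2 / 5 / 10% of 11,200 = 224 / 560 / 1,120, which bound those above. Design effect = 1 + 0.025(N/280 − 1); effective N = N / design effect; SE = √(4 × 0.025 × 0.975 / effective N); power = Φ(0.01/SE − z).

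Example, N = 9,520: design effect 1.825, effective N 5,216, SE 0.00432, power Φ(2.313 − 1.645) = 74.8%.

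| Patients analysed | Power, one-sided 5% | Power, one-sided 2.5% |
|---|---|---|
| 11,200 (no loss) | 77.8% | 67.4% |
| 9,520 (15% without eForm) | 74.8% | 63.8% |
| 9,296 (−224) | 74.3% | 63.2% |
| 8,960 (−560) | 73.6% | 62.4% |
| 8,400 (−1,120) | 72.2% | 60.8% |

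The second power column applies if the 95% interval in SAP 10.2.2 is two-sided. The cost against 9,520 is 0.5 to 2.6 points in the first column and 0.6 to 3.0 in the second.

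**The case against.** The strongest reply is that requiring some agreement in date is a reasonable way to keep false links out. SAP 6.3.1 removes late panels, and SAP 5 accepts that it cannot be checked whether laboratory data arrived for every patient. One panel left in the data therefore does not prove that the eForm describes it. The theoretical definition in SAP 10.1.2 judges each diagnosis against the panel's indications, so a false link can misclassify the outcome, and random misclassification tends to draw the arms together in a non-inferiority comparison. This stands as a reason to restrict a key-only rule, to count panels before exclusions and to test its effect. It does not justify dropping an unambiguous pair.

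Two smaller replies also carry weight. Typing errors are given as only part of the cause, and a key-only rule cannot help where the key itself fails. A double match stays within one patient, so its effect on a patient-level proportion should be small.

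A reader might infer more than the documents support:

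- *That a substantial number of forms is discarded.* The sentence describes failures of the exact match, before rules (b) to (d) rescue many wrong dates.
- *That the physician-rated definition needs no panel, so every key-matched eForm could be kept.* The six-month window needs a reliable laboratory date, the typed date is the doubtful field, and the SAP 6.3.1 exclusions act on the panel date.
- *That the loss biases the comparison.* Nothing indicates that date errors differ by arm.

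**Conclusion.** The gap is real and its likely effect is modest. A received eForm can be excluded solely for a date error outside three patterns, for a patient in whom the key already identifies the panel, and the matching is not one-to-one. Single-panel patients are probably the larger group, since the protocol planned on one panel each and the SAP says only some have more, but no count is given.

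The cost is no more than about 0.5 to 3 power points over the assumed 2 to 10% range. That rests on the plan's error rate and physician-level ICC, on the 11,200 recruited at the SAP's check, and on the 15% meaning forms never received. SAP 10.3 does not say whether that figure was counted before or after linkage; if after, part of this loss is already inside it. Not every unlinked form would be recovered, because the key-only rule covers only patients with one panel and one eForm. This is a cheap improvement that keeps data already collected, and it does not show that the planned result would be wrong.

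**What to change.** In SAP 6.2, before database lock:

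1. Apply the rules in order, one-to-one among rows not yet linked, nearest date first.
2. Add rule (e): if the key matches and the patient has exactly one laboratory panel, counted before the SAP 6.3.1 exclusions, and exactly one eForm, link them. Use the laboratory's panel date for the six-month window, then apply the exclusions.
3. Report the number linked by each rule and the number unlinked, separately from the 15% with no eForm. Give these by arm once the allocation is released.
4. Repeat the diagnostic-error analysis without the rule (e) links as a sensitivity analysis.

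The interviews follow the same procedure, so the ordering and counts should extend to them.

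The cost is a few lines of linkage code and one extra analysis. The downside is an occasional false link where the eForm describes a panel absent from the laboratory data. Counting panels before exclusions reduces that risk, and the sensitivity analysis shows whether it matters.
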